#### Modified Intent-To-Treat (mITT) population

The modified Intent-To-Treat (mITT) population will include all subjects who meet the inclusion/exclusion criteria, who use study product at least once and have data from at least one post baseline QoL questionnaire to support at least one of the secondary endpoint assessments (i.e. have a non-missing response in the 'Western Ontario and McMaster University Osteoarthritis Index' or 'EQ-5D-5L Quality of Life Questionnaire' eDiary pages). The mITT population will be used for all efficacy analysis.

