## 7.4 Analysis Variables

### 7.4.1 Disposition

Subject disposition data are collected on the 'Study Termination' eCRF page. Subjects are recorded as "Completed", "Screening failure", or "Early withdrawal". The date of the disposition event, date of last application of study drug and, if applicable, the date of death is recorded.

If applicable, the primary reason for discontinuation may include any of the following:

- Adverse Event (with a drop down to specify the AE number);
- Death;
- Inclusion not met/ Exclusion criteria met;
- Lack of efficacy;
- Lost to follow-up;
- Non-compliance with study drug;
- Occurrence of pregnancy;
- Physician's decision;
- Protocol violation;
- Withdrawal of consent;
- Withdrawal due to no pain;
- Other (with a free text to specify).

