## **7.4.7 Efficacy Variables**

### **7.4.7.1 Primary Efficacy Variable**

For primary analysis, average minutes of MVPA on Day 7 will be calculated over all non-missing days between study day 1 (product usage) through 7, inclusive and it is collected via the Actigraph device. Average minutes of MVPA on Day 14 will be calculated over all non-missing days between study day 8 through 14, inclusive. Average minutes of MVPA on Day 21 will be calculated over all non-missing days between study day 15 through 20, inclusive. Any days beyond day 20 will be excluded from all summaries and analyses and will only be present in listed data.

Average baseline MVPA is computed as:

- Average baseline MVPA = total minutes of MVPA over the baseline period / number of days with non-missing data over the baseline period.
  - Baseline period is defined in section 7.1.

Average MVPA for each 7-day period is calculated as:

- Average MVPA for 7-day period = total minutes of MVPA over the period / number of days with non missing data over the period.
  - If every day within the 7 – day period has non missing data, then the Average MVPA for 7- day period will be computed as: total minutes of MVPA over the period / 7.

Change from baseline is calculated as:

- Average MVPA for 7-day period - Average baseline MVPA.

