### 8.2 Specific Methods for Efficacy Analyses

For the primary and secondary endpoints where the data is collected through the activity tracker, only subjects who meet the minimum wear threshold will be included in the analysis. This is defined as a minimum of 3 valid days during the baseline period and a minimum of 3 valid days within each post-baseline 7-day period, where a valid day is defined as a minimum wear of 20 hours per day.

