#### 8.2.2 Primary Analysis

The primary efficacy endpoint is the average MVPA at Days 7, 14 and 21 as detailed in section 7.4.7.1.

The primary analysis will follow a hierarchical approach as follows:

1. A Mixed Model with Repeated Measures (MMRM) is used to analyse the change from baseline in MVPA average minutes as the response variable with baseline as a fixed effect. Subjects will be included as a random effect, and timepoint will be treated as a

repeated measure within each subject (with compound symmetry structure between visits). If the parameter for the intercept is found to be statistically significant (p-value < 0.05), then the second model below will be used.

2. A Mixed Model with Repeated Measures (MMRM) is used to analyse the change from baseline in MVPA average minutes as the response variable with baseline and timepoint (with unstructured covariance structure between visits) as fixed effects. Adjusted means for each timepoint will be presented along with p-values and 95% confidence intervals (CIs) for the mean change from baseline in MVPA.

Other than the global test for an overall change from baseline (i.e., intercept), there will be no other adjustment for multiplicity. If data are found to be non-normal, the Friedman Test will be used. If the Friedman test is found to be significant then Wilcoxon Signed Rank Pairwise Tests are used for each week comparison.

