### 8.2.5 Statistical/Analytical Issues

#### 8.2.5.1 Handling of Dropouts or Missing Data

In the derivation of endpoints there is no replacement of missing data except for adverse event dates as detailed in section 7.2.2.

The primary and secondary analysis method employs mixed-model with repeated measures analysis techniques which use information from the observed data, likelihood-based estimation, subject-specific effects and the within-subject correlation structure to provide information about the unobserved data (although missing data are not explicitly imputed). This analysis uses the available data to provide information about the unobserved data and estimates the treatment effects assuming the withdrawn subjects has the same statistical behaviour as those who continue. Data is not imputed for this type of analysis.

Missing data due to general dropout/withdrawals will be assessed on an ongoing basis during the study. Any further sensitivity analyses needed due to missing data will be reviewed at the time of data review.

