### 10.6 Efficacy Results

#### 10.6.1 Primary Efficacy Analysis

Table **CCI** summarizes change from baseline in the average minutes of MVPA at day 7, day 14 and day 21 by summary statistics by timepoint along with the analysis results specified in section 8.2.2 for the mITT.

Figure **CCI** presents MVPA over time for the mITT.

Listing **CCI** presents all MVPA data for the mITT.

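### The SAP 8.2 wear rule removes a subject from every tracker analysis for one deficient week, so the primary MMRM becomes a complete-case analysis reported as mITT

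*SAP*

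**What the plan says.** SAP 8.2 states, for the primary and secondary endpoints that come from the activity tracker, that "only subjects who meet the minimum wear threshold will be included in the analysis". It defines the threshold as "a minimum of 3 valid days during the baseline period and a minimum of 3 valid days within each post-baseline 7-day period", a valid day being one with at least 20 hours of wear.

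Other sections describe a different analysis:

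- SAP 6.1 defines the mITT by eligibility, one use of product and one post-baseline questionnaire, with no wear condition, and adds: "The mITT population will be used for all efficacy analysis".
- SAP 10.6.1 presents the primary summary "along with the analysis results specified in section 8.2.2 for the mITT".
- SAP 8.2.5.1 justifies the handling of missing data for the primary and secondary analyses thus: "This analysis uses the available data to provide information about the unobserved data". It assumes that withdrawn subjects behave like those who continue.
- SAP 7.4.7.1 shortens the third period: "Average minutes of MVPA on Day 21 will be calculated over all non-missing days between study day 15 through 20, inclusive".

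Protocol 13.3.1 averages MVPA over non-missing days with no wear threshold. SAP 3.5, which lists departures from the protocol, mentions only the mITT definition.

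**The concern.** The rule selects subjects, not weeks. Nothing says that a deficient week is set to missing while the subject stays in. A subject with two complete weeks who stops wearing the device on Day 16 contributes nothing to the primary analysis or to any tracker secondary. NRS and WOMAC carry no wear rule and are unaffected.

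The excluded subjects may differ in outcome. SAP 7.4.1 lists both lack of efficacy and "Withdrawal due to no pain" as reasons for leaving. Protocol 8.1 keeps subjects who are discontinued from treatment in the study, whereas Protocol 9.2.2 and 9.2.3 have subjects who stop early conclude it. Who is lost, and in which direction they differ, therefore cannot be settled from the documents. At stake is whether the headline result describes the mITT or a self-selected subset of it, and whether the stated missing-data justification applies to it.

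**Working it through.** **1. The plan's sample size.** Inputs from SAP 3.2.1: two-sided α 0.05, power 80%, standardised effect 0.25, Wilcoxon signed-rank test, 25% dropout.

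- Paired normal formula: ((1.960 + 0.842)/0.25)² = 125.6.
- Divided by the minimum relative efficiency of the Wilcoxon test, 0.864: 146 (148 with the noncentral t). The plan's 147 is reproduced within rounding.
- Dropout: 146/0.75 gives 195, the plan's enrolment (147/0.75 = 196). The allowance is 195 − 147 = 48 subjects.

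**2. What the rule requires.** Four conditions must hold together: at least 3 valid days at baseline, in Days 1–7, in Days 8–14 and in Days 15–20. The earliest possible third valid day in the last window is Day 17. Every subject who passes has all three weekly averages, so the tracker MMRM has no missing response.

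**3. Data discarded.** Assume 195 enrolled and 25% dropout spread evenly over the three weeks. A per-week rule leaves about 179, 163 and 148 subjects at Weeks 1, 2 and 3, before any wear failure. The rule as written leaves about 148 at each week. It discards about 179 − 148 = 31 Week 1 averages and 163 − 148 = 15 Week 2 averages.

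**4. Possible bias.** Assumptions: no true effect; three weekly changes with SD 1 and correlation 0.7; loss of Weeks 2 and 3 by a logistic model with slope 0.5 or 1.0 per SD of change; worse responders leave (signs reverse if better responders leave). Simulated with 2,000,000 subjects. Paired entries are for slopes 0.5 / 1.0.

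| Loss | Depends on | Estimate | Week 1 | Week 2 | Week 3 |
|---|---|---|---|---|---|
| 25% | Week 1 change | complete-case | 0.119 / 0.212 | 0.083 / 0.149 | 0.082 / 0.147 |
| 25% | Week 1 change | all valid weeks | 0.00 | 0.00 | 0.00 |
| 25% | Week 2 change | complete-case | 0.083 / 0.148 | 0.119 / 0.212 | 0.082 / 0.148 |
| 25% | Week 2 change | all valid weeks | 0.00 | 0.062 / 0.115 | 0.024 / 0.047 |
| 10% | Week 1 change | complete-case | 0.048 / 0.090 | 0.034 / 0.063 | 0.033 / 0.062 |

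A hand check for slope 0.5: if loss depends on the Week 1 change, the later weeks shift by 0.7 × 0.119 = 0.083. The likelihood estimate with all Week 1 data subtracts exactly that amount: 0.083 − 0.7 × 0.119 = 0.00. If loss depends on the unobserved Week 2 change, the correction is only about 0.7 × 0.083 = 0.058, so about 0.119 − 0.058 = 0.06 remains.

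An equal mix of the two directions gives about 0.00. Adding the baseline covariate of SAP 8.2.2, with an assumed correlation of −0.3 with change, moves these figures by about 0.01 SD at most.

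**5. Wear failure without dropout.** Assume daily validity varies between subjects as a Beta distribution with intraclass correlation 0.3. The table gives the percentage of subjects kept now / with a per-week rule, by number of candidate baseline days.

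| Mean daily validity | 3 days | 4 | 5 | 6 | 7 |
|---|---|---|---|---|---|
| 90% | 78.3 / 79.2 | 87.7 / 89.5 | 90.8 / 93.5 | 92.1 / 95.5 | 92.8 / 96.6 |
| 80% | 59.6 / 61.3 | 73.5 / 77.3 | 78.9 / 84.6 | 81.4 / 88.6 | 82.6 / 91.0 |

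The per-week rule recovers 0.8 to 3.8 points at 90% validity and 1.7 to 8.4 points at 80%. With a 3-day baseline most of the loss occurs at baseline and stays. Subjects who drop out after a valid Week 1 are recovered in addition to these.

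**The case against.** The strongest reply is that a week-by-week threshold was intended. Sections 7.4.7.1, 8.2.5.1 and 10.6.1 all fit that intention, and the detailed output specifications are in a separate shell document. The defect would then be one loosely worded sentence. That may be so, but a programmer who follows SAP 8.2 exactly deletes subjects, and the SAP contains no sentence that says otherwise.

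Second, the wear rule is openly pre-specified and can be read as a specific limit on the general mITT statement; even the repaired rule drops mITT subjects without a valid baseline. This has some force. The conflict with the mITT labelling is partly a matter of naming the analysed set and stating its size. The conflict with SAP 8.2.5.1 remains for the tracker endpoints.

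Third, the sample size already budgets for 147 completers. That protects power against dropout, but it does not make a complete-case estimate the planned one.

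Fourth, the bias figures are assumption-driven, and placing all of the 25% between a valid Week 1 and Day 17 is an upper-end case. This stands: at 10% loss the shift is 0.03 to 0.09 SD, and with mixed directions it is about zero. Nor is the analysed set strictly one of study completers. A subject who leaves on Day 18 with valid Days 15–17 stays in, while a completer with one poorly worn week is dropped.

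**Conclusion.** The concern holds. Read as written, SAP 8.2 turns the primary MMRM and every other tracker MMRM into an analysis of complete cases on baseline and all three periods. That contradicts SAP 8.2.5.1 and does not match the mITT label in SAP 6.1 and 10.6.1. This conclusion rests on the text and on no assumed number.

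The size is not known. The simulated shifts reach roughly half to most of the 0.25 design effect in Week 1 under the 25% scenario (0.12/0.25 = 48%; 0.21/0.25 = 84%) and are much smaller at 10% loss. They depend on the assumed correlation, slopes and timing, and the sign is open. Keeping all valid weeks removes the bias fully only if loss depends on observed data. If it depends on the unobserved Week 2 change, about half of the Week 2 bias remains. Because the rule decides who is in the primary analysis, it must be corrected before the analysis is run.

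**What to change.** 1. Apply the 3-valid-day threshold per period. Require a valid baseline, set only a deficient week to missing, and keep in the MMRM every mITT subject with at least one valid post-baseline week. Name this set, report its size in the tracker tables, and list the wear rule in SAP 3.5.
2. Report the all-weeks-valid subset as a sensitivity analysis.
3. SAP 8.2.2 also says: "If data are found to be non-normal, the Friedman Test will be used". That test needs all weeks from each subject and stays complete-case. If it is triggered, report beside it per-week Wilcoxon signed-rank tests of change from baseline on all available subjects. These restore only the weeks a subject has. With loss after Week 1, the tests for Weeks 2 and 3 still use the same subjects as the complete-case analysis.
4. As a clarification, state that only days with at least 20 hours of wear enter the baseline and weekly averages. SAP 7.1 and 7.4.7.1 speak only of non-missing days. This also settles whether the partial dispensing day counts when the baseline is shorter than 7 days.
5. Reconcile Protocol 8.1 with 9.2.2 and 9.2.3 on whether subjects who stop treatment remain under observation.

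Items 1 to 4 cost SAP wording, derivation code, the sensitivity output and, if the fallback is used, one supportive table. No new data are needed. The drawbacks are that some weekly means will rest on as few as 3 days, and that subjects who fail the baseline threshold are not recovered.

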#### 8.2.1 Hypothesis and Testing Strategy

The primary and secondary efficacy endpoint analyses aim to demonstrate that there is a difference between baseline and post-baseline in the variable of interest for each endpoint. More formally, the following hypothesis will be tested:

$H_0$ : There is no difference between baseline and post-baseline (Days 7, 14 and 21) in the endpoint of interest.

$H_1$ : There is a difference between baseline and post-baseline (Days 7, 14 and 21) in the endpoint of interest.

#### 8.2.2 Primary Analysis

The primary efficacy endpoint is the average MVPA at Days 7, 14 and 21 as detailed in section 7.4.7.1.

The primary analysis will follow a hierarchical approach as follows:

1. A Mixed Model with Repeated Measures (MMRM) is used to analyse the change from baseline in MVPA average minutes as the response variable with baseline as a fixed effect. Subjects will be included as a random effect, and timepoint will be treated as a

repeated measure within each subject (with compound symmetry structure between visits). If the parameter for the intercept is found to be statistically significant (p-value < 0.05), then the second model below will be used.

2. A Mixed Model with Repeated Measures (MMRM) is used to analyse the change from baseline in MVPA average minutes as the response variable with baseline and timepoint (with unstructured covariance structure between visits) as fixed effects. Adjusted means for each timepoint will be presented along with p-values and 95% confidence intervals (CIs) for the mean change from baseline in MVPA.

Other than the global test for an overall change from baseline (i.e., intercept), there will be no other adjustment for multiplicity. If data are found to be non-normal, the Friedman Test will be used. If the Friedman test is found to be significant then Wilcoxon Signed Rank Pairwise Tests are used for each week comparison.

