### **13.3 Statistical Analyses**

Additional details of the proposed statistical analysis will be documented in the statistical analysis plan (SAP), which will be written following finalization of the protocol and prior

Property of Haleon - Confidential

May not be used, divulged, published or otherwise disclosed without the consent of  
Haleon

Clinical Protocol Template, TMF-187821, v11.0. Parent SOP: **CCI** [REDACTED]

to study analysis. This section is a summary of the planned statistical analyses of the most important endpoints including primary and key secondary endpoints.

All data extracted from Actigraph and subjective assessments may undergo visualisation, and graphs will be plotted wherever feasible. For instance, data pertaining to both the daily average number of steps taken and the daily average number of stairs climbed/descended will be presented in sets of charts, graphs, and heatmaps. This approach aims to enable a more thorough analysis, fostering a comprehensive understanding of intricate patterns, trends, and relationships embedded in the dataset. Further information will be provided in the statistical analysis plan (SAP).

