### 13.3.1 Primary Analysis

Total study duration is 28 days, with primary analysis performed post baseline (baseline is from Day -7 to Day 0). For primary analysis, average minutes of MVPA on Day 7 will be calculated over all non-missing days between study day 1 (product usage) through 7, inclusive.

Average minutes of MVPA on Day 14 will be calculated over all non-missing days between study day 8 through 14, inclusive. Average minutes of MVPA on Day 21 will be calculated over all non-missing days between study day 15 through 21, inclusive. Any days beyond day 21 will be excluded from all summaries and analyses and will only be present in listed data.

A Mixed Model with Repeated Measures (MMRM) will be used to analyse the change from baseline in MVPA average minutes as the response variable. Subjects will be included as a random effect, and timepoint will be treated as a repeated measure within each subject. If data are found to be non-normal, an appropriate non-parametric test will be performed. If the parameter for the intercept (with compound symmetry structure between visits) is found to be statistically significant ( $p\text{-value} < 0.05$ ), then the individual timepoints (with unstructured covariance structure between visits) will be added as a fixed effect and adjusted means for each timepoint will be presented. P-values and 95% confidence intervals (CIs) for the mean change from baseline in MVPA will be obtained and presented for each timepoint. Other than the global test for an overall change from baseline (i.e., intercept), there will be no other adjustment for multiplicity.

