### 8.2.3 Secondary Analysis

The following secondary endpoints are analysed in the manner as described for the primary endpoint described in section 8.2.2:

- Change from baseline on Days 7, 14, and 21 in Daily Average number of steps taken.
- Change from baseline on Days 7, 14, and 21 in Ratio of sedentary/non-sedentary time.
- Change from baseline on Days 7, 14, and 21 in Gait, assessed through speed and step irregularity (measured via cadence and gait speed).
- Change from baseline on Days 7, 14, and 21 in Indices of morning stiffness (assessed through levels of mobility 30- and 60-mins post-wake).
- Change from baseline in self-reported pain intensity, assessed through Numeric Rating Scale (NRS) on Days 7, 14 and 21.
- Change from baseline in WOMAC Physical Function subscale on Days 7, 14, and 21.
- Change from baseline in the WOMAC subscales, Pain (composite) and Stiffness (composite) on Days 7, 14, and 21.
- Change from baseline in the WOMAC Global Score on Days 7, 14, and 21.

The secondary endpoint, study subjects' perceived ability to exercise more regularly, assessed using the WOMAC Physical Function subscale on Days 7, 14, and 21, will be analysed by exploring the correlation between WOMAC Physical Function subscale on Days 7, 14, and 21 and the average MVPA as detailed in section 7.4.7.1 (primary endpoint variable) graphically, by means of Spearman rank correlation.

The following secondary endpoints are analysed by descriptive statistics with no formal statistical hypothesis testing performed:

- MVPA on each day of the study (Baseline to final treatment day 21).
- Change from baseline in Karolinska Sleepiness Scale on Days 7, 14, and 21.
- Change from baseline in Health-related quality of life, EQ-5D-5L, on Days 7, 14, and 21.

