#### 8.2.5.3 Multiple Comparisons/Multiplicity

No account for multiple comparisons or multiple testing is performed, as a hierarchical strategy is applied for the primary efficacy endpoint as detailed in section 8.2.2.

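### Step 1 of the primary analysis tests the intercept of a model that contains baseline, so it does not test the mean change from baseline

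*SAP*

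**What the plan says.** SAP 8.2.1 sets the null hypothesis: "There is no difference between baseline and post-baseline (Days 7, 14 and 21) in the endpoint of interest". SAP 8.2.2 tests it in two steps.

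- **Step 1** is a repeated-measures model for change in average MVPA, "as the response variable with baseline as a fixed effect", with compound symmetry between visits. The rule for continuing is: "If the parameter for the intercept is found to be statistically significant (p-value < 0.05), then the second model below will be used".
- **Step 2** adds timepoint, uses an unstructured covariance, and reports adjusted means, p-values and confidence intervals for each week.

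The section then states: "Other than the global test for an overall change from baseline (i.e., intercept), there will be no other adjustment for multiplicity". SAP 8.2.5.3 leans on this: "No account for multiple comparisons or multiple testing is performed, as a hierarchical strategy is applied for the primary efficacy endpoint".

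SAP 8.2.3 extends the method beyond MVPA: "The following secondary endpoints are analysed in the manner as described for the primary endpoint described in section 8.2.2". The list covers steps, sedentary ratio, gait, morning stiffness, NRS pain, the WOMAC subscales and the WOMAC global score.

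Protocol 13.3.1 has the same intercept rule but names no baseline covariate. If the intercept is significant, "then the individual timepoints (with unstructured covariance structure between visits) will be added as a fixed effect". SAP 3.5, which lists changes from the protocol, records only the mITT definition.

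**The concern.** In a model with no covariates, the intercept of a change score is the mean change. Once baseline enters on its raw scale, the intercept becomes the expected change at a baseline of zero. For this trial that means a subject with no MVPA, or no knee pain, at entry. This is not the quantity in the null hypothesis.

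Two errors follow. For MVPA with no true change and ordinary regression to the mean, the intercept is positive, so step 1 passes far too often. For pain and WOMAC the real fall and the regression term have opposite signs, so step 1 can fail, or pass with the wrong sign, when symptoms have improved.

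Step 1 is the only protection offered for three weekly tests of the primary endpoint, and it decides whether step 2 is run at all.

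**Working it through.** **Inputs.** From the documents: two-sided 5% level, three weekly periods, compound symmetry in step 1, and 147 completers. The 147 is not in dispute: (1.96 + 0.84)² / 0.25² = 125.6, and dividing by the Wilcoxon minimum efficiency of 0.864 gives 145.3 (148.1 with the t version). Assumed, because the documents give none: normal data, baseline mean 60 minutes with SD 60 or 30 (only k = mean/SD = 1 or 2 matters), equal variances, one correlation ρ between all periods, no true change. Follow-up is taken as complete, which the wear rule in SAP 8.2 imposes for tracker endpoints. With complete data, step 1 is the regression of each subject's mean change on baseline.

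**What the intercept estimates.** With b the slope of follow-up on baseline:

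intercept = mean change + (1 − b) × mean baseline

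With no true change and equal variances, b = ρ, so the intercept is (1 − ρ) × 60. At ρ = 0.8 that is 12 minutes.

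**How often step 1 rejects when nothing has changed.** In SD units the residual variance of the three-week mean given baseline is v = (1 + 2ρ)/3 − ρ², and

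SE(intercept) = SD × √[v(1 + k²)/n]

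For ρ = 0.8 and SD 30: v = 0.8667 − 0.64 = 0.2267; SE = 30 × √(0.2267 × 5/147) = 2.63; z = 12/2.63 = 4.56; rejection probability Φ(4.56 − 1.96), about 99%. Simulation (6000 trials per cell) agrees with the formula:

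| ρ | Mean intercept, no change | Step 1 rejects | Step 1 rejects and at least one week significant |
|---|---|---|---|
| 0.5 | 30 | 100% | 12–13% |
| 0.7 | 18 | 99–100% | 12–13% |
| 0.8 | 12 | 94–99% | 10–13% |
| 0.9 | 6 | 68–86% | 7–10% |
| 0.95 | 3 | 38–57% | 5–7% |

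Ranges run over k = 1 to 2. The last column uses the ordinary standard error of each raw weekly change. With no step 1 at all it would be 12–13% throughout. With the protocol's step 1 (no baseline) it is 4–5%.

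**Mixed-model check.** One simulated data set (n = 147, SD 30, ρ = 0.8, no true change), fitted by REML with a random subject intercept, gave an intercept of 12.33 (SE 2.66, p < 0.001) with raw baseline. Without baseline it gave 0.32 (SE 1.28), which is the raw mean change.

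**Centring alone.** The intercept then equals the mean change, but its SE treats the baseline mean as fixed. The SE is too small by √{v / [(1 + 2ρ)/3 + 1 − 2ρ]}, which at ρ = 0.5 is √(0.4167/0.6667) = 0.79. The test then rejects in 12% of null trials at ρ = 0.5, 8–9% at 0.7 and about 6% at 0.9 to 0.95.

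**Pain (NRS).** Assumed: a 1.5-point fall every week, Day 0 mean 5.5, residual SD 2, residual correlation 0.6, n = 147. A test of mean change has 100% power. The intercept is −1.5 + (1 − b) × 5.5, which is zero at b = 0.73.

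| Slope b | 0.4 | 0.5 | 0.6 | 0.7 | 0.8 | 0.9 | 1 |
|---|---|---|---|---|---|---|---|
| Day 0 scores spread over 4–7: step 1 rejects | 70% | 41% | 17% | 6% | 9% | 26% | 55% |
| Day 0 scores spread over 2–9: step 1 rejects | 100% | 92% | 48% | 7% | 19% | 73% | 98% |

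At slopes of 0.6 or below, almost every rejection has a positive intercept, which points to worsening.

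**WOMAC pain (0–100).** Assumed mean 50, SD 15, a 15-point fall and residual SD 15. The intercept is −15 + (1 − b) × 50, zero at b = 0.70. Step 1 rejects in 98, 76, 27, 5, 26, 76 and 98% of trials at slopes 0.4 to 1, with the wrong sign up to 0.6.

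**The case against.** The strongest reply is that the SAP never says baseline is uncentred. It does say the intercept is meant as the test of overall change, so a programmer could centre to honour that. This is fair as far as it goes, but a covariate entered as written is on its raw scale, and the parameter that controls the primary analysis should not depend on a guess. Centring also leaves a test that rejects too often at low correlation.

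Second, the 38–100% figures are not false claims; the decision-level error is the fair measure, and it depends on the correlation pattern. If the post-baseline weeks correlate more with each other (0.9–0.95) than with baseline (0.7–0.9), the error is about 5–10%, against 9–11% with no step 1. At mean/SD 0.5 and a common ρ of 0.8 it is about 7%. This stands, and it limits the size of the problem.

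Third, MVPA is probably skewed, and the SAP sends non-normal data to the Friedman test, which bypasses the intercept. That is right, but the SAP gives no rule for judging normality, and the model remains the specified primary analysis.

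Fourth, even the protocol's version controls error only when no week differs from baseline. The step 2 point estimates are not biased by step 1, and SAP 10.6.1 and 10.6.2 tabulate summary statistics by timepoint regardless. All of this stands. The pain and WOMAC figures rest on several assumed inputs and show what can happen, not what is expected.

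**Conclusion.** The concern holds. As written, step 1 tests the expected change at a baseline of zero, not the null hypothesis in SAP 8.2.1, and describing it as the global test of change is wrong. That conclusion is algebra and needs no assumed figures.

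The size does depend on assumptions. Under those set out above, step 1 gives the three weekly MVPA tests almost no protection up to ρ of about 0.8 and partial protection at 0.9 to 0.95. A model without baseline would hold the error at 4–5% when no week has changed. For pain and WOMAC, step 2 may not be run despite a real improvement when the fall is close to (1 − b) × the baseline mean.

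The damage is to the p-values and to whether step 2 results exist, and it arises only on the parametric route. Because this step decides the primary test and is the stated reason for no other multiplicity adjustment, it must be corrected before the models are run.

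**What to change.** 1. **Step 1:** remove baseline from the fixed effects, as in protocol 13.3.1, so that the intercept is the mean change. Do not rely on centring alone.
2. **Step 2:** estimate the weekly changes without the baseline covariate, or fit baseline and the three weeks as four repeated outcomes with unstructured covariance and test each week against baseline. This is a separate, conditional point. The SAP does not say where adjusted means are evaluated. At the sample-mean baseline with the usual SE, and with equal variances, the SE is too small by √[(1 + ρ)/2].
3. **Secondary endpoints:** make the same change for every endpoint in SAP 8.2.3 that follows the primary method.
4. **Smaller points:** state that baseline is one of the levels in the Friedman fallback, or use a signed-rank test on each subject's mean change as the first step. List any remaining departure from the protocol in SAP 3.5.

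The cost is SAP wording and a few lines of code. If step 2 would otherwise have used adjusted means at the sample-mean baseline, its confidence intervals widen by √[2/(1 + ρ)]: about 15% at ρ = 0.5, 8% at 0.7 and 3% at 0.9. Under equal variances that is their proper width.
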